2.0 OBJECTIVES

2.1 Primary Objectives

To evaluate the response rates for patients with advanced NSCLC with mutations in the target genes for nintedanib.

2.2 Secondary Objectives

- 1. To evaluate progression free survival.
- 2. To correlate outcomes with specific mutations.
- 3. To further evaluate extreme responders with exome and transcriptome sequencing.
- 4. To evaluate the mechanisms of secondary resistance.

3.0 PATIENT SELECTION

3.1 Inclusion Criteria

1. Histologically confirmed diagnosis of advanced (metastatic or unresectable) NSCLC with mutations, rearrangement and fusion involving RET oncogene, or abnormalities (non-synonymous SNV or amplification) in the nintedanib target genes *VEGFR1-3*,

Protocol Version: 02/02/24 Page 16 of 57

- TP53, PDGFR-A, PDGFR-B, or FGFR1-3.CLIA certified lab testing for nintedanib target genes using cell free DNA from peripheral blood and/or assays performed on tumor tissues are acceptable
- 2. Patients with EGFR mutations or ALK rearrangements must have disease progression on appropriate FDA-approved therapy for these genomic aberrations prior to enrollment.
- 3. Disease progression on platinum-doublet chemotherapy prior to enrollment.
- 4. At least one measurable lesion or evaluable disease. Measurable disease is defined as lesions that can be accurately measured in at least one dimension (longest diameter to be recorded) as ≥10 mm with CT scan, as ≥20 mm by chest x-ray, or ≥10 mm with calipers by clinical exam.
- 5. Prior treatment of cancer (chemotherapy, radiation therapy, and surgery) is allowed if completed at least 3 weeks prior to start of treatment with nintedanib and if all treatment-related toxicities are resolved.
- 6. At least 18 years of age.
- 7. ECOG performance status 0-1 (see Appendix A).
- 8. Normal bone marrow and organ function as defined below:
 - a. Leukocytes $\geq 3,000/\text{mcL}$
 - b. Absolute neutrophil count ≥ 1,500/mcL
 - c. Platelets $\geq 100,000/\text{mcL}$
 - d. Hemoglobin $\geq 9.0 \text{ g/dL}$
 - e. INR < 2.0
 - f. PT and PTT < 50% of deviation from IULN
 - g. Total bilirubin $\leq 1.5 \text{ x IULN}$
 - h. $AST(SGOT)/ALT(SGPT) \le 1.5 \text{ x IULN}$ for patients without liver metastases and $\le 2.5 \text{ x IULN}$ for patients with liver metastases
 - i. Urine protein < 2+
 - j. Creatinine within normal institutional limits

Creatinine clearance > 45 mL/min for patients with creatinine levels above institutional normal

9. Women of childbearing potential and men must agree to use adequate contraception (hormonal or barrier method of birth control, abstinence) prior to study entry, for the duration of study participation, and for 3 months after the end of treatment. Should a woman become pregnant or suspect she is pregnant while participating in this study, she must inform her treating physician immediately.

Protocol Version: 02/02/24 Page 17 of 57

10. Able to understand and willing to sign an IRB approved written informed consent document (or that of legally authorized representative, if applicable).

3.2 Exclusion Criteria

- 1. Prior treatment with *VEGFR* tyrosine kinase inhibitors.
- 2. A history of other malignancy ≤ 5 years previous with the exception of basal cell or squamous cell carcinoma of the skin which were treated with local resection only or carcinoma *in situ* of the cervix.
- 3. Currently receiving any other investigational agents, or received an investigational agent within 3 weeks of the first dose of nintedanib.
- 4. Radiotherapy to the target lesion within the past 3 months prior to baseline imaging.
- 5. Symptomatic brain metastases. Patients with known brain metastases are eligible if the metastases are asymptomatic and previously treated.
- 6. Leptomeningeal disease.
- 7. Radiographic evidence of cavitary or necrotic tumors.
- 8. Centrally located tumors with radiographic evidence (CT or MRI) of local invasion of major blood vessels.
- 9. A history of allergic reactions attributed to compounds of similar chemical or biologic composition to nintedanib or other agents used in the study.
- 10. Uncontrolled intercurrent illness including, but not limited to, ongoing or active infection, symptomatic congestive heart failure > NYHA II, active coronary artery disease, unstable angina pectoris, serious cardiac arrhythmia, uncontrolled hypertension (defined as systolic pressures > 150 mmHg or diastolic pressure > 90 mmHg), pericardial effusion, uncontrolled seizure disorder, or psychiatric illness/social situations that would limit compliance with study requirements.
- 11. Major injuries and/or surgery with then past 4 weeks prior to the start of study treatment with incomplete wound healing and/or planned surgery during the on-treatment study period.
- 12. History of clinically significant hemorrhagic or thromboembolic event in the past 6 months.
- 13. Known inherited predisposition to bleeding or thrombosis.

Protocol Version: 02/02/24 Page 18 of 57

- 14. History of cardiac infarction within the past 12 months prior to the start of study treatment.
- 15. Receiving therapeutic anticoagulation (except low-dose heparin and/or heparin flush as needed for maintenance of an in-dwelling intravenous device) or anti-platelet therapy (except for low-dose therapy with acetylsalicylic acid < 325 mg QD).
- 16. Pregnant and/or breastfeeding. Patients of childbearing potential must have a negative pregnancy test within 14 days of study entry.
- 17. Significant weight loss (> 10% of BW) within past 6 months prior to inclusion into the trial.
- 18. Known active or chronic hepatitis B or C infection.
- 19. Active alcohol or drug abuse.
- 20. Gastrointestinal disorder or abnormality that would interfere with absorption of the study drug.
- 21. Known HIV-positivity on combination antiretroviral therapy because of the potential for pharmacokinetic interactions with nintedanib. In addition, these patients are at increased risk of lethal infections when treated with marrow-suppressive therapy. Appropriate studies will be undertaken in patients receiving combination antiretroviral therapy when indicated.

3.3 Inclusion of Women and Minorities

Both men and women and members of all races and ethnic groups are eligible for this trial.

4.0 REGISTRATION PROCEDURES

Patients must not start any protocol intervention prior to registration through the Siteman Cancer Center.

The following steps must be taken before registering patients to this study:

- 1. Confirmation of patient eligibility by Washington University
- 2. Registration of patient in the Siteman Cancer Center database
- 3. Assignment of unique patient number (UPN)

Once the patient has been entered in the Siteman Cancer Center OnCore database, the WUSM coordinator will forward verification of enrollment and the UPN via email.

Protocol Version: 02/02/24 Page 19 of 57

4.1 Confirmation of Patient Eligibility

Confirm patient eligibility by collecting the information listed below and scanning and emailing it to the research coordinator listed in the *Siteman Cancer Center Clinical Trials Core Protocol Procedures for Secondary Sites* packet at least one business day prior to registering patient:

- 1. Your name and contact information (telephone number, fax number, and email address)
- 2. Your site PI's name, the registering MD's name, and your institution name
- 3. Patient's race, sex, and DOB
- 4. Three letters (or two letters and a dash) for the patient's initials
- 5. Current approved protocol version date
- 6. Copy of signed consent form (patient name may be blacked out)
- 7. Planned date of enrollment
- 8. Completed eligibility checklist, signed and dated by a member of the study team
- 9. Copy of appropriate source documentation confirming patient eligibility

4.2 Patient Registration in the Siteman Cancer Center OnCore Database

Registrations may be submitted Monday through Friday between 8am and 5pm CT. Urgent late afternoon or early morning enrollments should be planned in advance and coordinated with the Washington University research coordinator. Registration will be confirmed by the research coordinator or his/her delegate by email within one business day. Verification of eligibility and registration should be kept in the patient chart.

All patients at all sites must be registered through the Siteman Cancer Center OnCore database at Washington University.

4.3 Assignment of UPN

Each patient will be identified with a unique patient number (UPN) for this study. Patients will also be identified by first, middle, and last initials. If the patient has no middle initial, a dash will be used on the case report forms (CRFs). All data will be recorded with this identification number on the appropriate CRFs.

5.0 TREATMENT PLAN

5.1 Agent Administration

Nintedanib is an oral drug which will be administered on an outpatient basis at a dose of 200 mg twice daily during each 28-day cycle. Starting with cycle 64, cycles will last 12 weeks. Patients should take nintedanib approximately 12 hours apart at around the same time every day after food intake. Capsules should not be opened and should be swallowed unchewed with approximately 8oz of water. If a patient misses a dose, the patient should

Protocol Version: 02/02/24 Page 20 of 57

be instructed not to take or make up that dose and to resume dosing with the next scheduled dose. Patients will be instructed to bring all unused capsules and their medication diary to each study visit for assessment of compliance.

5.2 General Concomitant Medication and Supportive Care Guidelines

Diarrhea should be treated at first signs with adequate hydration and anti-diarrheal medicinal products, e.g. loperamide, and may require interruption, dose reduction, or discontinuation of therapy.

Supportive care for nausea and vomiting may include medicinal products with anti-emetic properties, e.g. glucocorticoids, antihistamines, or 5-HT3 receptor antagonists and adequate hydration. In the event of dehydration, administration of electrolytes and fluids is required. Plasma levels of electrolytes should be monitored if relevant GI AEs occur. Interruption, dose reduction, or discontinuation of therapy may be required despite appropriate supportive care.

If co-administered with nintedanib, strong P-gp inhibitors, e.g. ketoconazole or erythromycin, may increase exposure to nintedanib. In such cases, patients should be monitored closely for tolerability of nintedanib.

Strong P-gp inducers, e.g. rifampicin, carbamazepine, phenytoin, and St. John's Wort, may decrease exposure to nintedanib. Co-administration with nintedanib should be carefully considered.

5.3 Women of Childbearing Potential

Women of childbearing potential are required to have a negative pregnancy test within 14 days prior to the first dose of nintedanib. Women will be considered to be of childbearing potential unless surgically sterilized by hysterectomy or bilateral tubal ligation/salpingectomy, or post-menopausal for at least two years.

Female and male patients (along with their female partners) are required to use a highly effective method of birth control during participation in the study and for 3 months following the last dose of nintedanib. A highly effective method of birth control is defined as one which results in a low failure rate (i.e. less than 1% per year) when used consistently and correctly, such as implants, injectables, combined oral contraceptives, some intrauterine devices (IUDs), sexual abstinence, or vasectomized partner.

If a patient is suspected to be pregnant, nintedanib should be immediately discontinued. In addition, a positive urine test must be confirmed by a serum pregnancy test. If it is confirmed that the patient is not pregnant, the patient may resume dosing.

Protocol Version: 02/02/24 Page 21 of 57

If a female patient or female partner of a male patient becomes pregnant during therapy or within 3 months after the last dose of nintedanib, the investigator must be notified in order to facilitate outcome follow-up.

5.4 **Duration of Therapy**

If at any time the constraints of this protocol are considered to be detrimental to the patient's health and/or the patient no longer wishes to continue protocol therapy, the protocol therapy should be discontinued and the reason(s) for discontinuation documented in the case report forms.

In the absence of treatment delays due to adverse events, treatment may continue until one of the following criteria applies:

- Documented and confirmed disease progression
- Death
- Adverse event(s) that, in the judgment of the investigator, may cause severe or permanent harm or which rule out continuation of study drug
- General or specific changes in the patient's condition render the patient unacceptable for further treatment in the judgment of the investigator
- Suspected pregnancy
- Serious non-compliance with the study protocol
- Lost to follow-up
- Patient withdraws consent
- Investigator removes the patient from study
- The Siteman Cancer Center decides to close the study
- NCCN decides to close the study

Patients who prematurely discontinue treatment for any reason will be followed as indicated in the study calendar.

5.5 **Duration of Follow-up**

There is a 28-day follow-up visit following the last dose of study drug. Patients will be monitored as per routine care thereafter for progression and survival, and that data will be captured in the case report forms. Patients removed from study for unacceptable adverse events will be followed until resolution or stabilization of the adverse event.

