10.0 STUDY CALENDAR

All visits have a window of \pm 3 days.

	Screening	Day 1 of Each Cycle	End of Every Cycle	End of Treatment
Informed consent	X	-		
H&P, ECOG PS	X	X		X
CBC ⁶	X	X		X
CMP^7	X	X		X
Coagulation panel ⁸	X			
Urinalysis ⁹	X			
Pregnancy test	X^1			
CT scan – chest and abdomen with contrast	X		X	
Nintedanib		X^2		
Fresh biopsy for research sequencing ³				X^4
Adverse events assessment	X	X X ⁵		

- 1. Women of childbearing potential only; serum or urine
- 2. Taken twice a day every day of each 28-day cycle. Starting with cycle 64 cycles will last 12 weeks.
- 3. If a biopsy is obtained for clinical purposes at the time of disease progression, a sample may be collected for research purposes
- 4. To be monitored for 28 days after end of treatment
- 5. One follow-up visit at 28 days after end of treatment, then routine follow-up as per standard of care, with data collection regarding progression and survival to take place for the study
- 6. CBC with differential includes: WBCs, RBCs, Hemoglobin, Hematocrit, MCV, MCH, MCHC, RDW-CV, Platelets, MPV, Absolute Neutrophils, Lymphocytes, Monocytes, Eosinophils, and Basophils
- 7. CMP includes: Sodium, Potassium, Carbon Dioxide, BUN, Glucose, Creatinine, Calcium, Chloride, Albumin, AST, ALT, Alkaline Phosphatase, Bilirubin, Plasma Protein and Anion Gap
- 8. CoAg panel includes PT, PTT, and INR
- 9. Urinalysis includes: Color, Clarity, Specific Gravity, pH, Protein, Glucose, Ketones, Bilirubin, Blood, Urobilinogen, Nitrites and Leukocyte Esterase

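### The only scheduled pregnancy test precedes the first dose; on treatment and at End of Treatment, detection depends on self-report or clinical suspicion.

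*Combined protocol and SAP*

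**What the plan says.** Three places set the pregnancy test, and all place it before treatment.

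- Section 5.3: "Women of childbearing potential are required to have a negative pregnancy test within 14 days prior to the first dose of nintedanib".
- Section 3.2, exclusion 16: "Patients of childbearing potential must have a negative pregnancy test within 14 days of study entry".
- Section 10.0, Study Calendar: the pregnancy-test row has one mark, under Screening. Footnote 1 reads "Women of childbearing potential only; serum or urine"; it sets who is tested and on what sample, and adds no repeat.

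On treatment, the plan reacts to suspicion. Inclusion 9 obliges the woman to tell her physician if she is, or thinks she is, pregnant. Section 5.3 then says "If a patient is suspected to be pregnant, nintedanib should be immediately discontinued", and adds that "a positive urine test must be confirmed by a serum pregnancy test". Section 5.4 lists suspected pregnancy among the reasons to stop. It sets no maximum duration: "treatment may continue until one of the following criteria applies". Section 5.1 provides for cycle 64 and beyond.

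**The concern.** Section 1.3.1 reports teratogenicity in rats, with a steep dose-effect relationship and early embryofetal deaths at low doses, at plasma concentrations similar to or lower than those in patients. The protocol answers this hazard with contraception, a stop rule and outcome follow-up. The stop rule works only once somebody suspects a pregnancy, and no scheduled procedure after the first dose tests for one.

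Suspicion is a weak trigger with this drug. Section 1.3.2 gives drug-related nausea in 57.5% and vomiting in 42.5% of the phase II NSCLC patients, and section 1.6 lists fatigue as a risk. The same symptoms in early pregnancy could easily be put down to nintedanib.

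What is at stake is participant safety, specifically how long an unrecognised pregnancy stays exposed. Response rate, PFS and the sample size of 20 are untouched.

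**Working it through.** **1. Is there a later test anywhere?** The plan gives no figure to reproduce, so the first check is a reading of the schedule.

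- Calendar: one test at Screening; none on Day 1 of Each Cycle, End of Every Cycle or End of Treatment, and none specified for the 28-day follow-up.
- Recurring chemistry: "CMP includes: Sodium, Potassium, Carbon Dioxide, BUN, Glucose, Creatinine, Calcium, Chloride, Albumin, AST, ALT, Alkaline Phosphatase, Bilirubin, Plasma Protein and Anion Gap". No pregnancy marker. The CBC list in footnote 6 has none either.
- Urinalysis: "Urinalysis includes: Color, Clarity, Specific Gravity, pH, Protein, Glucose, Ketones, Bilirubin, Blood, Urobilinogen, Nitrites and Leukocyte Esterase". No pregnancy marker, and it is done at Screening only.
- The sentence in 5.3 on confirming a positive urine test says what to do with a result. It does not schedule a test.

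The calendar table was read from PDF, but 5.3 and exclusion 16 independently describe a pre-treatment test only, so the single mark is not a reading error.

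**2. Chance of pregnancy on treatment.** Inputs: failure rate of 1% per year (5.3's threshold for a highly effective method); treatment length of 11.6 weeks (median PFS in ECOG 0–1 patients, 1.3.2), used as an illustrative fixed duration.

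- 11.6 × 7 = 81.2 days; 81.2 / 365.25 = 0.222 years.
- 1 − 0.99^0.222 = 0.22% per woman.
- If all 20 patients were women of childbearing potential: 20 × 0.0022 ≈ 0.045 expected pregnancies. The actual number of such women is not given and may be zero.

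**3. Days of dosing after conception, given that conception occurs on treatment.** Assumptions: conception is uniform over days 0–81.2; a test turns positive L = 10 or 14 days after conception (not in the documents); Day 1 tests of cycles 2 and 3 fall 28 and 56 days after the first dose; otherwise exposure ends at day 81.2.

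| Conception interval, L = 10 | Exposure ends | Length × mean exposure |
|---|---|---|
| 0–18 | day 28 | 18 × 19 = 342 |
| 18–46 | day 56 | 28 × 24 = 672 |
| 46–81.2 | day 81.2 | 35.2 × 17.6 = 619.5 |

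Mean = 1633.5 / 81.2 = 20.1 days; maximum = 56 − 18 = 38 days.

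For L = 14 the breakpoints are days 14 and 42: 14 × 21 + 28 × 28 + 39.2 × 19.6 = 294 + 784 + 768.3 = 1846.3. Mean = 1846.3 / 81.2 = 22.7 days; maximum = 42 days.

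With no test and no suspicion: mean = 81.2 / 2 = 40.6 days; maximum = 81.2 days. This is an upper bound, because a Day 1 visit or the patient may raise the question sooner.

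**4. Longer treatment.**

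- Without testing: 63 × 28 = 1,764 days (4.8 years) pass before cycle 64 with no scheduled test.
- With Day 1 testing through cycle 63: undetected exposure is capped at L + 28 = 38–42 days. If one visit is 3 days early and the next 3 days late, the cap is L + 34 = 44–48 days.
- From cycle 64, with 12-week cycles: L + 84 = 94–98 days.

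**The case against.** The sponsor can fairly say this is a deliberate and consistent choice. The plan has a chain of controls: a negative test before dosing, highly effective contraception during the study and for 3 months after, a duty to report, an immediate stop on suspicion, serum confirmation and outcome follow-up. Patients are examined every 28 days through cycle 63, and nothing in the documents requires repeat testing.

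The numbers are also small. Even with 20 women of childbearing potential, about 0.045 expected pregnancies times a saving of 18–20.5 days (40.6 minus 22.7 or 20.1) is under one exposure-day across the trial. The no-suspicion comparator overstates the saving by an unknown amount. Monthly testing still leaves about three weeks of mean exposure, although the rat findings stress early harm. The End of Treatment test changes no exposure figure, because dosing has already stopped.

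Most of this stands as a statement about weight: absolute risk is low, the modelled saving is a ceiling, and the earliest exposure cannot be prevented. It does not close the gap, since every on-treatment control still starts with suspicion.

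Two points go the other way. The 1% figure presumes consistent, correct use, while inclusion 9 accepts barrier methods without that threshold, so 0.22% is not a safe upper limit. The End of Treatment test has a separate purpose: it helps find pregnancies that began on therapy, whose outcomes 5.3 wants followed.

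**Conclusion.** The concern holds. The plan schedules one pregnancy test, before the first dose, and none afterwards, although treatment is open-ended and the protocol itself describes the drug as teratogenic in animals. That the tests are missing is certain from the text.

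The size is less certain. The probability of pregnancy is low (about 0.22% per woman over 11.6 weeks at 1% per year). Given conception on treatment, Day 1 testing would roughly halve the worst-case mean exposure, from 41 to 20–23 days, and reduce the maximum from 81 to 38–42 days. Those figures rest on the assumed 10–14 day detection lag, uniform conception and a fixed treatment length borrowed from another study. The change is recommended because the potential harm is serious and irreversible and the cost is slight. It does not bear on the validity of the trial's results.

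**What to change.** For women of childbearing potential, add to the Study Calendar and section 5.3:

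- a negative urine or serum pregnancy test on Day 1 of every cycle, before drug is dispensed. The Cycle 1 test also covers the interval of up to 14 days since the screening test;
- a pregnancy test at End of Treatment.

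Keep 5.3's serum confirmation of any positive urine test, and state that drug is held until that result is known.

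The cost is two more marks in an existing calendar row and one sentence in 5.3. Through cycle 63 it means about 13 tests per woman per year (365.25 / 28 = 13.0), and about 4 per year from cycle 64 (365.25 / 84 = 4.3). All fall at existing visits, and a serum test can use blood already drawn for the CBC and CMP. The downside is an occasional false positive with a short hold; 5.3 already lets a patient resume once pregnancy is ruled out. If no woman of childbearing potential enrols, no extra test is done.

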6.0 DOSE DELAYS/DOSE MODIFICATIONS

6.1 Criteria for Interruption of Treatment with Nintedanib

Treatment with nintedanib has to be interrupted in case any of the criteria listed in the table below is fulfilled.

Protocol Version: 02/02/24 Page 22 of 57

If one criterion is met, nintedanib has to be interrupted

- nausea of CTCAE grade ≥ 3 despite supportive care
- vomiting of CTCAE grade ≥ 2 despite supportive care
- diarrhea of CTCAE grade ≥ 2 for more than 3 consecutive days despite supportive care
- AST and/or ALT of CTCAE grade ≥ 2 in conjunction with bilirubin of CTCAE grade ≥ 1
- AST and/or ALT of CTCAE grade ≥ 3
- other non-hematological adverse event of CTCAE grade ≥ 3 considered drugrelated

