The predominant adverse events were nausea, diarrhoea, vomiting, abdominal

Protocol Version: 02/02/24 Page 12 of 57

pain and fatigue of mostly low to moderate intensity after monotherapy with nintedanib (BIBF1120). Dose limiting toxicities were dose dependent hepatic enzyme elevations that were reversible after discontinuation of nintedanib (BIBF1120) treatment. These liver enzyme elevations were only in few cases accompanied by a simultaneous increase of bilirubin. In general common terminology criteria for adverse events (CTCAE version 3, grade three liver enzyme increases were reported in the dose groups of 250 mg twice daily or higher. They also were reversible and usually occurred within the first two months of treatment.

Hypertension or thromboembolic events were rare and did not suggest an increased frequency as a consequence of therapy with nintedanib (BIBF1120).²¹

LUME-Lung 2 was a similar randomised, double-blind, phase III study of nintedanib plus pemetrexed versus placebo plus pemetrexed in patients with advanced non-squamous non-small cell lung cancer after failure of first line chemotherapy.

Based on a preplanned futility analysis of investigator-assessed PFS, enrolment was halted after 713/1300 planned patients had been enrolled. The analysis (based on conditional power for PFS by investigator assessment) suggested that the study was futile and that the primary endpoint of centrally assessed PFS would likely not be met. The futility analysis was based on conditional power; there was no formal testing of null hypothesis as planned for primary analysis no safety issues were identified.

Even though the study was stopped prematurely, the primary endpoint of this Phase III trial was met; treatment with nintedanib plus pemetrexed resulted in a significant prolongation of centrally reviewed PFS compared with placebo plus pemetrexed (median PFS 4.4 vs. 3.6 months with a HR 0.83; p=0.0435). The disease control rate was also increased significantly in nintedanib-treated patients. There was no improvement in OS in nintedanib-treated patients. Nintedanib 200 mg bid in combination with pemetrexed had an acceptable and manageable safety profile, with no new or unexpected safety findings. The most frequent AEs were reversible increases in liver enzymes and gastrointestinal events.²⁵

Ovarian Cancer

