1.6 Benefit – Risk Assessment

Although considerable progress has occurred in understanding the biological characteristics of cancer as well as the development of more effective treatment regimens, most patients with locally advanced or metastatic tumors succumb to their disease. Thus, there is a substantial need for novel therapeutic strategies to improve the outcome for patients with advanced or metastatic non-small cell lung cancer.

Antiangiogenic treatment with the orally available triple angiokinase inhibitor nintedanib (BIBF1120) with inhibition of VEGFR, PDGFR, RET and FGFR offers the chance to control both locally recurrent and distant metastatic disease on an outpatient basis. Treatment with nintedanib (BIBF1120) may have the potential to provide significant benefit to patients with locally advanced and/or metastatic non-small cell lung cancer by slowing tumor progression and metastasis, since its cellular target is expressed on the tumor vasculature in most malignancies. Induction of endothelial cell apoptosis may result in subsequent degradation of tumor vessels and subsequent tumor necrosis. Additionally, tumor growth may be affected by direct anti-tumour effects, e.g. tumor cells that express VEGFR, PDGFR, RET, or FGFR.

The risks of therapy with nintedanib (BIBF1120) in adult patients are primarily related to:

- the gastro-intestinal tract (nausea, vomiting, diarrhea, abdominal pain)
- increases in liver enzymes (AST, ALT, γ-GT)
- fatigue, asthenia and anorexia.

Liver enzymes must be followed closely during treatment with nintedanib (BIBF1120).

Therapy with the trial drugs must be interrupted in the event of relevant hepatic toxicity and further treatment is to be withheld until recovery of the abnormal laboratory parameters.

Protocol Version: 02/02/24 Page 15 of 57

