6.2 Criteria to Restart Nintedanib

A patient is eligible to restart nintedanib if all criteria listed in the table below are met.

If a patient has to interrupt intake of nintedanib due to an adverse event for more than 14 days, the decision to restart treatment with nintedanib needs to be discussed and agreed upon between the investigator and the study supporter.

All criteria have to be met in order to restart nintedanib

- nausea CTCAE grade ≤ 2
- vomiting CTCAE grade ≤ 1
- diarrhoea CTCAE grade < 2
- AST and ALT CTCAE grade ≤ 2 and bilirubin CTCAE grade ≤ 1
- no other non-hematological adverse event grade CTCAE ≥ 3 which is considered drug-related

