6.3 Dose Adjustments of Nintedanib

As initial measure for the management of side effects, treatment with nintedanib should be temporarily interrupted until the specific adverse reaction has resolved to levels that allow continuation of therapy. Nintedanib treatment may be resumed at a reduced dose. Dose adjustments in 100 mg steps per day (i.e. a 50 mg reduction per dosing) based on individual safety and tolerability are recommended as described in the sections above. In case of further persistence of the adverse reaction(s), i.e. if a patient does not tolerate 100 mg twice daily, treatment with nintedanib should be discontinued.

The following dose levels will be used in case dose adjustments are required for management of undue toxicity.

Protocol Version: 02/02/24 Page 23 of 57

Dose-level:	0	-1	-2	-3
Dose:	200 mg BID	150 mg BID	100 mg BID	Discontinue

Of note:

If the dose of nintedanib had to be reduced due to toxicity, it will stay on the lower dose level for the entire time of administration.

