7.6.2 Adverse Events of Special Interests (AESI)

The following events are considered as protocol-specified events of special interests:

Any gastrointestinal- and non-gastrointestinal perforation, leakage, fistula formation, abscess

In such case the following additional information need to be collected, documented in the respective comment field of the CRF page and the respective narratives of the SAE. That has to be forwarded to Boehringer Ingelheim:

- Location of perforation, leakage, fistula, abscess
- Location/extent of abdominal tumor manifestations,
- Imaging & reports (CT, ultrasound, endoscopy, pathology, etc.)
- Prior surgery (location, wound healing complications)
- Concomitant diseases with GI involvement (e.g., M Crohn, vasculitis, tuberculosis, diverticulitis)
- Thromboembolic events (or predisposition)

Drug-induced liver injury is under constant surveillance by sponsors and regulators and is considered a protocol-specified adverse event of special interest (AESI). Timely detection, evaluation, and follow-up of laboratory alterations of selected liver laboratory parameters to distinguish an effect of the investigational drug from other causes are important for patient safety and for the medical and scientific interpretation of the finding.

The following are considered as protocol-specified AESI:

- An elevation of ALT and / or AST > 5x ULN without bilirubin elevation measured in the same blood draw sample
- An elevation of AST and/or ALT >2.5 fold ULN combined with an elevation of bilirubin to >1.5 fold ULN measured in the same blood draw sample

Protocol Version: 02/02/24 Page 29 of 57

Patients showing above laboratory abnormalities need to be followed up until the protocol specific retreatment criteria have been met and according to Appendix C of this clinical trial protocol.

Protocol-specified AESI are to be reported in an expedited manner similar to Serious Adverse Events, even if they do not meet any of the seriousness criteria.

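### AST or ALT at grade 2 with bilirubin at grade 1 must stop nintedanib under 6.1, yet meets the liver restart line of 6.2 with no change in values

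*Combined protocol and SAP*

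**What the plan says.** Section 6.1 sets a mandatory rule in which any single item suffices: "If one criterion is met, nintedanib has to be interrupted". Two of its items concern the liver: "AST and/or ALT of CTCAE grade ≥ 2 in conjunction with bilirubin of CTCAE grade ≥ 1" and "AST and/or ALT of CTCAE grade ≥ 3".

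Section 6.2 makes a patient eligible to restart when every item on its list is met. The liver item is "AST and ALT CTCAE grade ≤ 2 and bilirubin CTCAE grade ≤ 1". If an adverse event has kept the patient off drug for more than 14 days, the investigator and the study supporter must agree on the restart. Shorter interruptions carry no such requirement there.

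Three other places bear on the point:

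- Section 6.3 has treatment "temporarily interrupted until the specific adverse reaction has resolved to levels that allow continuation of therapy".
- Section 1.6 says that after relevant hepatic toxicity "further treatment is to be withheld until recovery of the abnormal laboratory parameters".
- Section 6.4 lists grade 2 AST or ALT with raised bilirubin as a dose-reduction event. The first episode takes the dose from 200 to 150 mg twice daily, the second to 100 mg twice daily, and the third ends treatment. These adjustments are required only for drug-related events.

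**The concern.** A restart rule should describe a state in which the stopping rule no longer applies. Here the two liver rules share a state, so a patient can be stopped and be eligible to resume without any laboratory value having moved. On resuming, the same patient must be stopped again at once.

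Reversible enzyme elevation is the main dose-limiting toxicity described in Section 1.3.2, so the liver row is the one where the rules most need to agree. A restart within 14 days gets no second opinion under 6.2.

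The restart levels are also used elsewhere. Under Section 7.6.2, and again in Appendix C, patients with the specified liver abnormalities "need to be followed up until the protocol specific retreatment criteria have been met". If that phrase is read as the 6.2 levels, close liver follow-up could end while 6.1 still requires the drug to be withheld.

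**Working it through.** The plan gives no figure to reproduce; the check is one of logic.

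**Inputs.** Let T be the higher of the AST and ALT grades and B the bilirubin grade, each from 0 to 4, giving 5 × 5 = 25 combinations.

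- Interrupt (I), from 6.1: (T ≥ 2 and B ≥ 1) or T ≥ 3.
- Restart (R), from the 6.2 liver item: T ≤ 2 and B ≤ 1.

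| T | B = 0 | B = 1 | B = 2 | B = 3 | B = 4 |
|---|---|---|---|---|---|
| 0 | R | R | – | – | – |
| 1 | R | R | – | – | – |
| 2 | R | **I and R** | I | I | I |
| 3 | I | I | I | I | I |
| 4 | I | I | I | I | I |

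**Counts.**

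- Interrupt: 4 combinations at T = 2, plus 2 × 5 = 10 at T = 3 or 4, giving 14.
- Restart: 3 × 2 = 6.
- Both: 1, at T = 2 and B = 1.
- Neither: 6. Check: 14 + 6 − 1 + 6 = 25.

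Treating AST and ALT separately gives 125 triples. Five of them satisfy both rules, written as (AST, ALT, bilirubin): (0,2,1), (1,2,1), (2,0,1), (2,1,1) and (2,2,1). All five are the same state, T = 2 and B = 1.

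**Can the whole 6.2 list be met in that state?** Yes. An isolated liver event leaves the nausea, vomiting, diarrhea and other non-hematological items satisfied.

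**Do the other rows overlap?** Compared by grade, interruption against restart:

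- nausea: ≥ 3 against ≤ 2
- vomiting: ≥ 2 against ≤ 1
- diarrhea: ≥ 2 against < 2
- other drug-related non-hematological events: ≥ 3 against none ≥ 3

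None shares a grade. The 6.2 liver item mirrors the T ≥ 3 trigger but does not account for the combined transaminase and bilirubin trigger, which suggests a drafting slip.

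**Does the corrected line work?** With restart defined as (T ≤ 2 and B = 0) or (T ≤ 1 and B ≤ 1), the allowed combinations are (0,0), (1,0), (2,0), (0,1) and (1,1). That is 5, with none in the interrupt set. Only (2,1) is lost from the present line.

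**The case against.** The strongest reply is that 6.1 is a standing rule, not one confined to the onset of an event, and that 6.2 only makes a patient eligible. On that reading a patient at T = 2 and B = 1 still may not be dosed, and unchanged values have neither resolved in the sense of 6.3 nor recovered in the sense of 1.6. This shows what was intended, and a careful investigator would probably wait. But 6.3 and 1.6 give no liver grade, and 6.2 is the only place that states restart levels. If 6.1 governs throughout, the 6.2 line is wrong for this state.

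Section 6.4 softens the consequence. A drug-related episode brings a lower dose on restart, and the number of episodes is limited. That stands, but 6.4 sets the dose and not the time of restart, and a patient resumed at 150 mg twice daily in this state still meets 6.1.

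It can also be said that one combination in 25 is not a rate, that this is a descriptive pilot of 20 patients, and that the chemistry panel is repeated on day 1 of each cycle. All true, and these facts limit the importance of the point.

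Finally, Section 3.1 admits patients with total bilirubin up to 1.5 times the upper limit of normal, so some might never return to bilirubin grade 0. For them the corrected line leaves the route through AST and ALT at grade 1 or lower. It asks nothing that 6.1 does not already ask.

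**Conclusion.** The concern holds. The liver items of 6.1 and 6.2 contradict each other in exactly one state, grade 2 for the higher of AST and ALT with grade 1 bilirubin. The finding depends only on the two rules as written and needs no assumption about how often each grade occurs.

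The documents do not give the frequency of this state. It is probably low: Section 1.3.2 reports that enzyme elevations were "only in few cases accompanied by a simultaneous increase of bilirubin" and that most hepatic dose-limiting cases arose at 250 mg and above, while this trial starts at 200 mg twice daily. The rule permits a restart; it does not compel one. No effect on the response-rate analysis is claimed. This is a safety-rule inconsistency that should be corrected, not a threat to the trial's conclusions.

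**What to change.** Reword the liver item of 6.2 as: *AST and ALT both grade 2 or lower with bilirubin grade 0, or AST and ALT both grade 1 or lower with bilirubin grade 1 or lower.* Keeping the present item and adding a condition that no interruption criterion in 6.1 is currently met would have the same effect. Section 7.6.2 and Appendix C refer to the retreatment criteria, so they follow the corrected rule without further edits.

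The cost is one line in a minor amendment, with no extra patients or procedures. The few patients in this state may be held longer, until bilirubin returns to grade 0 or AST and ALT fall to grade 1 or lower. The documents do not allow that extra time to be estimated.

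The change does not touch the six combinations that neither rule covers (AST and ALT at grade 1 or lower with bilirubin at grade 2 or higher), which are a separate matter.
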